### 7.4 Efficacy

#### Parasitology

- **Asexual parasite counts**

Microscope blood slides will be prepared prior to the first dose of DHA-PQP at screening on Day 1 to confirm the diagnosis of *P. vivax* malaria, and then twice a day, 6-12 hours apart for the first 3 days, or until 2 consecutive negative thick blood smears are obtained. Where the subject receives DHA/PQP < 6 hours from midnight on Day 1, a second Day 1 slide may be omitted.

Microscope blood slides will be prepared at subsequent visits on Days 7, 14, 21, 28, 60, 90, 120, 150 and 180 (refer to Section 7.1 Time and Events table). In addition, blood films should be obtained whenever parasitological re-assessment is required and at the relapse visit or withdrawal visit as applicable. For detailed instructions on the methodology for staining and counting please refer to the SRM.

Slides are considered negative after review of 100 high-power fields. A negative slide refers to the absence of asexual parasites only.

- **Gametocyte counts**

In the same way, thick film slides will be read for gametocytes on Day 1 (prior to the first dose of DHA-PQP) and then twice a day 6-12 hours apart for the first 3 days or until 2 consecutive negative thick blood smears are obtained. Slides will be prepared at subsequent visits on Days 7, 14, 21, 28, 90, 120, 150 and 180 (refer to Section 7.1 Time and Events Table).

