2.3. Study Design

Overview of Study Design and Key Features	

The diagram illustrates the study timeline. It begins with 'Informed Consent Signed' at Day 1. The 'Screening' phase occurs on Day 1. The 'Treatment Period' lasts for 14 days, starting on Day 1 or Day 2, during which participants receive DHA-PQP (Days 1-3) plus blinded treatment. 'Treatment Completed' is marked at the end of the 14-day period. The 'Follow-Up Period' includes visits on Days 21, 28, 60, 90, 120, 150, and 180. Outcomes include 'Relapse**' and 'Withdrawal - attend w/d visit'. For subjects who do not relapse by Day 180, there is an 'Open label-PQ (only for subjects who do not relapse)' phase leading to a 'Day 195***' visit. 'Withdrawn from Treatment' also leads to 'Follow-Up Assessments (Days 21-180)'.
	

Open label DHA-PQP 3 or 4 tablets per day (according to weight) on Days 1-3 plus blinded study treatment as follows:
 
 1) Tafenoquine 300 mg single dose on Day 1 and placebo for primaquine on Day 1-14* 2) Primaquine 15mg on Days 1-14 and placebo for tafenoquine on Day 1* 3) Placebo for tafenoquine on Day 1 and placebo for primaquine on Days 1-14* 
* Blinded study treatment will start on Day 1 or Day 2 and continue for 14 days ** Subjects who relapse before D180 will receive immediate rescue treatment (ACT + PQ 0.5mg/kg daily for 14 days) and attend FU visits ***Subjects who do not relapse before D180 will receive open label PQ (0.5mg/kg daily for 14 days) and return for Day 195 visit
	
Design Features	
A double-blind, double-dummy, randomized, parallel group, placebo-controlled superiority study.
 
Approximately 150 participants will be enrolled from the Indonesian army returning from deployment in a heavily malarious region of Indonesia.
 
Duration of study: Up to 195 days, including screening (Day 1), and randomization to treatment (Day 1 or Day 2), 14 daily visits while receiving blinded study treatment and seven follow-up visits (Days 21, 28, 60, 90, 120, 150 and 180). Participants who do not relapse by Day 180 will attend a follow up visit on Day 195, following 14 days of open label primaquine.

Dosing	
All participants will receive open label DHA-PQP on Study Days 1-3, together with TQ or PQ and matching placebo beginning on Study Day 1 or 2. TQ, or matching placebo, will be given as a single 300mg dose. Participants will receive PQ, 15mg once daily, or matching placebo, for 14 days.

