5.3 Examination of Covariates, Other Strata and Subgroups

5.3.1 Covariates and Other Strata

Battalion, weight and baseline *P.vivax* asexual parasite count will be included as covariates in the time-to-event analysis of relapse-free efficacy at 6 months.

Battalion will be derived based on participant numbers as follows:

Battalion	Participant Numbers
Battalion 1	001-074
Battalion 2	075- 164

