7.2.5.1. Statistical Methodology Specification

Secondary Statistical Analyses
Endpoints / Variables
Relapse-free efficacy at 4 months

Secondary Statistical Analyses

Time to relapse Time to fever clearance Time to asexual parasite clearance Time to gametocyte clearance

Model Specification

mITT population Estimates for time to endpoint will be determined for each treatment group using Kaplan-Meier methods. Cox's proportional hazards analysis, including terms for battalion and treatment for calculation of Hazard Ratios for time to fever clearance, time to asexual parasite clearance, time to gametocyte clearance, and relapse-free efficacy at 4 months.

Model Checking & Diagnostics

The proportional hazards assumption should be assessed including a check of the Kaplan-Meier curves. The shape of the curves should be similar for the treatment groups with the separation between the curves remaining proportional across time. A complementary log-log plot may also be used to check the proportional hazards assumption. If the proportional hazards assumption is violated a logistic regression model will be performed instead using a binary response variable of event vs no event (e.g. fever clearance vs no fever clearance) and including battalion and treatment as covariates.

Model Results Presentation

Time to relapse is covered in Table 2.8. Tables 2.16 to Table 2.19: Number of participants with the endpoint and number censored Estimates for time to the endpoint: 1st quartile, median, 3rd quartile and associated 95% confidence intervals For the relapse-free efficacy at 4 months endpoint only, the Kaplan-Meier estimate and 95% confidence interval of the relapse-free efficacy rate for each treatment at 4 months. For time to parasite clearance, time to fever clearance and relapse-free efficacy at 4 months: Hazard ratio (TQ+DHA-PQP vs DHA-PQP only, TQ+DHA-PQP vs PQ+DHA-PQP and PQ+DHA-PQP vs DHA-PQP only) and 95% confidence interval. Kaplan-Meier survival curves will be produced for time to fever clearance (Figure 2.5), time to asexual parasite clearance (Figure 2.6), and time to gametocyte clearance (Figure 2.7).

Subgroup Analyses

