
Defined as: time needed to clear asexual parasite from the blood i.e. parasite numbers falling below the limit of detection in the thick blood smear and remaining undetectable ≥ 6 hours later.
 
If a participant has a non-zero asexual P. vivax parasite count at baseline, and prior to Study Day 8 has two negative counts with at least 6 hours between the counts and no positive parasite counts within this time period, parasite clearance time will be defined as the time elapsed between the first dose of study medication (including DHA-PQP) and the first of these negative counts (measured in hours).
 
Participants with a negative parasite count at baseline will be censored with a parasite clearance time of 0 hours. All other participants will be censored at the time of the last non-missing assessment prior to Study Day 8.

Gametocyte (GCT)

Defined as: time from first dose until the first slide that was gametocyte negative and remained so at the next slide reading.
 
Any participant with negative P. vivax gametocytes at baseline will be censored with a time to gametocyte clearance of 0 days.
 
For all other participants, gametocyte clearance will be considered to have been achieved once a negative gametocyte value has been seen, unless the next gametocyte count is positive. Time to clearance will then be defined as (time to first negative value) – (time of first dose of study medication including DHA-PQP).
 
Subjects who fail to reach this endpoint will be censored at the visit of their final gametocyte assessment.

Fever (FCT)

Defined as: time from first dose of treatment to the time when body temperature falls to normal and remains normal for at least 48 hours up to the Day 7 visit.
 
Any participant who does not have a temperature in excess of 37.4°C at any point prior to the first dose of study medication (including DHA-PQP) on Study Day 1 will be censored with a fever clearance time of 0 hours. Participants will also be censored at time 0 if the method of temperature measurement is not consistent throughout Study Days 1 to 7 (i.e., method is not consistently oral, tympanic, or axillary).
 
Fever clearance is considered to have been achieved once an initial temperature of >37.4°C is reduced to a value $\leq 37.4^\circ\text{C}$, in the absence of value >37.4°C in the following 48 hours

Clearance time

up to the Day 7 visit.

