Number needed to treat per treatment group before one extra
success was seen compared to DHA-PQP only

Xx (xx,xx)

Xx (xx,xx)

[1] Subjects are censored if they did not have *P.vivax* at baseline, or took a drug with anti-malarial action despite not having malaria parasites, or did not have a 6 month assessment.

[2] Kaplan-Meier methodology

[3] Estimated from Cox's Proportional Hazards Analysis, adjusting for Battalion.

A hazard ratio < 1 indicates a lower chance of relapse compared to DHA-PQP only.

Population: Microbiologic Intent-to-Treat

EFF_T3
 Logistic Regression Analysis of Relapse-Free Efficacy at 6 Months (Subjects Censored Prior to 6 Months Excluded)

Treatment Group	N	n	Subjects Relapse Free (%)	Subjects Relapsed (%)	Comparison with DHA-PQP Only		
					Adjusted Odds Ratio of Relapse	95% CI	p-value
TQ+DHA-PQP	Xx	Xx	Xxx (xx%)	Xxx (xx%)	x.xx	(x.xx, x.xx)	0.xxx
PQ+DHA-PQP	Xx	Xx	Xxx (xx%)	Xxx (xx%)	x.xx	(x.xx, x.xx)	0.xxx
DHA-PQP Only	Xx	xx	Xxx (xx%)	Xxx (xx%)			

Note: Model includes terms for battalion and treatment.
 An odds ratio <1 represents a smaller chance of relapse compared to DHA-PQP only.

Population: Microbiologic Intent-to-Treat

TTE3

Analysis of Time to <Asexual Parasite Clearance>

	TQ+DHA-PQP (N=xxx)	PQ+DHA-PQP (N=xxx)	DHA-PQP only (N=xxx)
Number of Subjects			
Relapse	xx (xx%)	xx (xx%)	xx (xx%)
Censored	xx (xx%)	xx (xx%)	xx (xx%)
Estimates for Time to Clearance (Days) [1]			
1st Quartile	xx.x	xx.x	xx.x
95% CI	(xx.x, xx.x)	(xx.x, xx.x)	(xx.x, xx.x)
Median	xx.x	xx.x	xx.x
95% CI	(xx.x, xx.x)	(xx.x, xx.x)	(xx.x, xx.x)
3rd Quartile	xx.x	xx.x	xx.x
95% CI	(xx.x, xx.x)	(xx.x, xx.x)	(xx.x, xx.x)
Adjusted Hazard Ratio vs DHA-PQP only [2]			
Estimate	x.xx	x.xx	
95% CI	(x.xx, x.xx)	(x.xx, x.xx)	
p-value	x.xxx	x.xxx	
Adjusted Hazard ratio vs PQ+DHA-PQP [2]			
Estimate	x.xxx		
95% CI	(x.xxx, x.xxx)		

[1] Kaplan-Meier methodology

[2] Estimated from Cox's proportional Hazards Analysis, adjusting for Battalion.
 A hazard ratio <1 indicates a lower risk of [endpoint] compared to DHA-PQP only.

Population: Microbiologic Intent-to-Treat

EFF_T4

Incidence of Genetically Homologous and Genetically Heterologous *P. vivax* Infections (determined by PCR)

	TQ+DHA-PQP (N=xx)	PQ+DHA-PQP (N=xx)	DHA-PQP only (N=xx)
n [1]	Xx	Xx	Xx
P. vivax classified as genetically heterologous by PCR	Xx (xx%)	Xx (xx%)	Xx (xx%)
P. vivax classified as genetically homologous by PCR	Xx (xx%)	Xx (xx%)	Xx (xx%)

[1] n = number of subjects with an infection

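### The Cox model for asexual parasite clearance leaves out the baseline parasite count, which may cost some precision and power in a secondary comparison

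*SAP*

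**What the plan says.** SAP 7.2.5.1 (secondary endpoints, Model Specification) calls for "Cox's proportional hazards analysis, including terms for battalion and treatment for calculation of Hazard Ratios for time to fever clearance", and the sentence goes on to asexual parasite clearance, gametocyte clearance and four-month relapse-free efficacy. In Appendix 12, shells TTE1 (relapse) and TTE3 (clearance) carry the same footnote apart from one capital letter: "Estimated from Cox's Proportional Hazards Analysis, adjusting for Battalion". SAP 7.2.5.1 plans no sensitivity analysis for these endpoints.

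SAP 11.6.3 defines asexual clearance time as "time needed to clear asexual parasite from the blood i.e. parasite numbers falling below the limit of detection in the thick blood smear". It runs from the first dose, DHA-PQP included, to the first of two negative counts at least 6 hours apart, before Study Day 8.

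The baseline count comes from the pre-dose smear (Protocol 7.4) and is covered by the baseline rule in SAP 5.2. SAP 5.3.1 assigns it to one endpoint only: "asexual parasite count will be included as covariates in the time-to-event analysis of relapse-free efficacy at 6 months". SAP 7.1.5.1 then uses it in a refit of the six-month relapse model.

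For asexual clearance, the text of SAP 7.2.5.1 asks for Kaplan-Meier quartiles, hazard ratios and 95% intervals. It asks for no p-value, although TTE3 has a row for one. Protocol 9.4.1 asks for statistical comparisons of parasite clearance time.

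**The concern.** The plan uses the baseline count where its link to outcome is indirect (relapse over six months) and omits it where the endpoint is read on that same count. At a given clearance rate, a man who starts with more parasites takes longer to reach the detection limit.

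Leaving a prognostic covariate out of a Cox model generally pulls the treatment hazard ratio towards 1 and can lower power. No stratification by count is described either. With 50 per arm, the standard error of the between-arm difference in mean log count is SD × √(2/50) = 0.2 SD, so about one trial in three will differ by more than that, and the planned model cannot adjust for it.

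At stake is how the blood-stage objective is read: a diluted hazard ratio or a wide interval could be taken to show that tafenoquine adds nothing to DHA-PQP in clearing parasites.

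**Working it through.** **1. The plan's own power figure.** Protocol 9.2.1 states more than 90% power for the primary endpoint only. With 45 per arm after 10% loss and relapse of 50% and 15%: HR = ln 0.85 / ln 0.50 = 0.2345; events = 45 × 0.65 = 29.25.
- Schoenfeld: Φ(½√29.25 × |ln 0.2345| − 1.96) = 97.5%.
- Freedman: Φ(√29.25 × (1 − 0.2345)/(1 + 0.2345) − 1.96) = 91.8%.
- Two proportions: 95.6%.

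The stated figure reproduces. There is no corresponding figure for clearance, so everything below rests on assumptions.

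**2. Benchmark with no prognostic covariate.** If all 100 men in two arms clear, Schoenfeld power is Φ(5 × ln HR − 1.96): 26% at HR 1.3, 53% at 1.5, 80% at 1.75 and 93% at 2.0.

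**3. Decay model.** Time = ln(baseline count / detection limit) / clearance rate, read on a twice-daily smear grid (Protocol 7.4: "then twice a day, 6-12 hours apart for the first 3 days"). There are 50 per arm and 600 runs per setting; the Monte Carlo standard error is about 2 points per estimate. R² is the share of variance in clearance time explained by log count.

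| SD of log10 count | CV of rate | R² | Clearance faster by | Power without count | Power with log count | Gain (points) |
|---|---|---|---|---|---|---|
| 0.5 | 0.5 | 0.18 | 15% | 20.3% | 21.0% | 0.7 |
| 0.5 | 0.5 | 0.18 | 25% | 38.0% | 42.5% | 4.5 |
| 0.7 | 0.5 | 0.29 | 15% | 15.5% | 21.2% | 5.7 |
| 0.7 | 0.5 | 0.29 | 25% | 37.7% | 44.8% | 7.1 |
| 0.7 | 0.3 | 0.51 | 15% | 20.2% | 27.8% | 7.6 |
| 0.7 | 0.3 | 0.51 | 25% | 51.2% | 66.8% | 15.6 |

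Over all settings tried (SD 0.3 to 0.7, CV 0.3 to 0.5, R² 0.08 to 0.52), the gain is 0 to 16 points at 25% faster and −2 to +8 at 15% faster. A variant with counts truncated to 20–100,000/µL and SD 0.5 to 0.9 (500 runs, 25% faster) gave 54/61%, 56/70% and 54/69% (without/with) at CV 0.3, and 39/41%, 39/47% and 37/48% at CV 0.5: gains of 2 to 15 points on these rounded figures.

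**4. Proportional hazards given the count, no ties.** 50 per arm, 3,000 runs; R² is on the log-time scale.

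| R² | HR 1.5: without / with | HR 1.75: without / with |
|---|---|---|
| 0 | 50% / 51% | 77% / 77% |
| 0.10 | 42% / 51% | 67% / 76% |
| 0.25 | 33% / 51% | 53% / 77% |
| 0.40 | 25% / 51% | 42% / 77% |
| 0.60 | 16% / 48% | 27% / 75% |

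With a true conditional HR of 1.5, the battalion-only estimate averages 1.44, 1.36 and 1.30 at R² 0.10, 0.25 and 0.40. A similar run at HR 1.6 to 2.0 and correlation 0.3 to 0.6 gave gains of about 10 points (71.5% to 81.7%) to 35 points (47.3% to 82.0%).

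**5. Smaller effects in the exponential model.** Correlation 0.3 to 0.5, 1,500 runs. Times 25% shorter (HR 1/0.75 = 1.33): gain 4 to 9 points. Times 15% shorter (HR 1/0.85 = 1.18): gain about 2 to 4 points. On a smear grid the gains are 5 to 8 and 1 to 2 points.

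**6. No treatment effect.** The model without the count rejects in about 3% to 6% of runs.

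**The case against.** A reader might infer that the baseline count by definition largely sets clearance time, so that the comparison loses substantial power. The documents do not support that. Under SAP 11.6.3 the time depends on both the starting count and the clearance rate, and no correlation or variance split is given. The entry floor of 20/µL (Protocol 5.1) and the hyperparasitaemia limits of 100,000 or 250,000/µL (Protocol Appendix 4) are eligibility bounds; they do not describe the spread among enrolled men.

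The large losses also need large effects. In an exponential model, HR 1.8 means clearance times 44% shorter (1 − 1/1.8). Yet every arm gets the same blood-stage drug ("All participants will receive open label DHA-PQP on Study Days 1-3, together with TQ or PQ and matching placebo"), and Protocol 4.4 describes tafenoquine as absorbed more slowly than ACTs. This stands, with one qualification: hazard ratio and percentage shortening do not map one to one. In the decay model, clearance 25% faster gave adjusted hazard ratios of 1.46 to 1.63 in the rows tabulated, because those times are less dispersed than exponential ones.

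It is also fair that no decision hangs on this power. SAP 5.4 names a single primary comparison, the test stays valid, and the interval already allows for chance imbalance on average. The pull towards 1 is partly the difference between a marginal and a conditional hazard ratio. Battalion plus treatment also matches the primary model.

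None of this is a reason to leave out an available covariate. It limits the size and rank of the point.

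**Conclusion.** The omission is real, and for asexual parasite clearance it is worth correcting. The size is uncertain. With 50 per arm and 15% to 25% faster clearance assumed, leaving out the count costs about nil to 16 points of power. Losses of 20 points or more appear only with larger assumed hazard ratios and a count that explains about a quarter or more of the variation. Type I error is unaffected. At small effects the comparison has low power with or without the covariate.

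The point should not be extended with equal force to the other clearance endpoints. Gametocyte-negative men "will be censored with a time to gametocyte clearance of 0 days", and men without baseline fever are likewise censored at 0, so those analyses rest on smaller subsets of unknown size and no gain has been computed for them. Gametocyte clearance is also missing from the list of hazard ratios to present in SAP 7.2.5.1.

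Severity: minor. The endpoint is secondary, with no power target or success rule.

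**What to change.** Before unblinding, specify in SAP 7.2.5.1 that the Cox model for asexual parasite clearance (Table 2.17) contains treatment, battalion and log10 baseline *P. vivax* asexual count. Change the TTE3 footnote to match, and report the battalion-only model as supportive. State which pre-treatment count enters the log: SAP 5.2 takes the latest value as baseline but calls a man positive if any pre-treatment count is positive. Men with a zero baseline count are censored at 0 hours and add nothing to the likelihood, so the undefined log loses no information.

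The cost is one term, already collected. The small downsides are a log-linear assumption for the covariate and a hazard ratio that is conditional on baseline count, which is why the battalion-only result should stay in view. Matching terms for baseline gametocyte count (among men positive at baseline) and baseline temperature are optional.

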#### 4.4. Design Justification

Selection of soldiers as study population: The study will be conducted in male soldiers diagnosed with *P.vivax* malaria following return to a malaria non-endemic area of Indonesia after a recent deployment to a heavily malarious region (e.g. Papua). This study model has been selected as it should provide a reliable estimate of the true relapse rate (rather than overall recurrence rate) following TQ co-dosed with DHA-PQP since in this setting recurrent parasitemias are most likely to arise from re-activated hypnozoites rather than re-infection. It is recognized that members of the armed forces are considered a vulnerable population for clinical trials [ICH Guidance for Industry. Guideline E6 ]. Special attention will be paid to ensuring that the commanders and troops understand the concept and importance of voluntary informed consent prior to commencing the study (See Section 7.2). The study will undergo appropriate ethics committee review.

This is a soldier study population and only male subjects will be recruited. However, the safety profile of TQ has also been evaluated in over 1000 females who participated in Phase I, II and III clinical studies. The data indicate similar tolerability of TQ in males and females with the exception of G6PD heterozygous females who are at increased risk of mild to moderate hemoglobin declines. The safety of TQ in this population is being evaluated in a separate study (Study TAF116564). TQ will be contraindicated in pregnant and lactating females.

Selection of ACT: DHA-PQP has high efficacy rates (>95%) for clearing the blood stage infection of *P.vivax* in regions of Indonesia where chloroquine resistance is common [Ratcliff, 2007, Hasugian, 2007]. Both DHA-PQP and artesunate –amodiaquine are first line treatments for *P.falciparum* and *P.vivax* in Indonesia, although DHA-PQP is preferred due to its superior efficacy and better tolerability compared to other ACTs [Hasugian, 2007] (See Section 4.5).

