4. ANALYSIS POPULATIONS

Population	Definition / Criteria	Analyses Evaluated
Screened	All participants who were screened for eligibility.	Study Population
Enrolled	All randomised participants.	Study Population
Safety	All randomised participants who received at least one dose of blinded study treatment. If participants receive a treatment different to their randomized treatment, they will be	Study Population Safety

Population	Definition / Criteria	Analyses Evaluated
	analysed according to the treatment actually received.	
Safety Open Label, PQ phase, Non-Relapsers (Safety OL)	All participants in the safety population who did not relapse during the double-blind phase and went onto the open-label primaquine phase at the end of the study.	Study Population Safety
Microbiologic-Intent-To-Treat (mITT)	All randomized participants who received at least one dose of blinded study treatment and have microscopically-confirmed P. vivax parasitaemia at baseline. Participants will be analysed according to their randomized treatment.	Efficacy
Per-Protocol (PP)	All participants in the mITT population for whom there were no major protocol deviations that impact the primary endpoint. Protocol deviations that would exclude participants from the PP population are defined in Section 4.1 (Protocol Deviations) and Appendix 1 (Protocol Deviation Management and Definition for Per-Protocol Population).	Sensitivity/ supporting analyses of efficacy data
PK population	All participants for whom at least one systemic tafenoquine concentration, and associated sample date/time is available.	PK

NOTES:

Please refer to [Appendix 11](#): List of Data Displays which details the population to be used for each display being generated.

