Participants who do not demonstrate this endpoint prior to final assessment of Study Day 3 will be censored at that time point.

Participants with missing data in Study Days 1-3 will be censored at the last available temperature assessment, if they do not meet the definition of fever clearance before the Day 7 visit.

CPD2D6 Activity and Metabolizer Phenotype

Eijkman Institute will provide CYP2D6 *alleles which will be used to derive metabolizer class (Poor metabolizer (PM), Intermediate metabolizer (IM), Extensive metabolizer (EM), Ultra metabolizer (UM)).

Each of the two CYP2D6 *alleles, comprising the genotype, will be assigned a value relative to its activity compared to the *1 reference allele:

Value of 0 for null activity alleles: *3, *4, *5, *6, *7, *8, *11, *15

Value of 0.5 for reduced activity alleles: *9, *10, *14, *17, *29, *41

Value of 1 for fully functional alleles: *1, *2, *35

For all *alleles that are not captured above, the activity score will be determined prior to unblinding the data.

Alleles denoting gene duplications, represented by 'xN', will receive double the non-duplicated value. For example, *1xN will receive a value of 2 whereas *1 receives a value of 1.

The CYP2D6 Activity Score (AS) [Gaedigk, 2008] is then calculated as the sum of activity values from the two alleles comprising the genotype. For example, a participant with 2 null alleles will have an AS of 0; one null and one reduced activity allele will have a score of 0.5; or one null allele and one fully functional allele will have an AS of 1.

The CYP2D6 phenotype will be classified based on the AS and follows the Dutch Pharmacogenomics Working Group [DPWG] classification scheme, where:

Poor metabolizer if AS = 0

Intermediate metabolizer if AS = 0.5 or 1

Extensive metabolizer if AS = 1.5 or 2

Ultra metabolizer if AS \geq 2.5

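### If proportional hazards fails, the SAP compares the clearance endpoints by whether men cleared, not how fast, with no rule for men who had no fever or gametocytes at baseline

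*SAP*

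**What the plan says.** SAP 7.2.5.1 (secondary analyses, model checking) plans a Cox model with battalion and treatment for the fever, asexual parasite and gametocyte clearance times in the mITT population. Proportional hazards is checked by looking at the Kaplan-Meier curves, with an optional complementary log-log plot. If the assumption is judged not to hold, the SAP's rule is this: "a logistic regression model will be performed instead using a binary response variable of event vs no event (e.g. fever clearance vs no fever clearance", again with battalion and treatment as covariates. The section plans no sensitivity analysis for these endpoints.

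SAP 11.6.3 sets the censoring rules:

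- **Fever.** A man with no temperature above 37.4°C before the first dose "will be censored with a fever clearance time of 0 hours". A second group joins him: "Participants will also be censored at time 0 if the method of temperature measurement is not consistent throughout Study Days 1 to 7". For febrile men who do not clear, "Participants who do not demonstrate this endpoint prior to final assessment of Study Day 3 will be censored at that time point".
- **Gametocytes.** A man who is negative at baseline "will be censored with a time to gametocyte clearance of 0 days".
- **Asexual parasites.** "Participants with a negative parasite count at baseline will be censored with a parasite clearance time of 0 hours". However, the mITT population in SAP section 4 is "All randomized participants who received at least one dose of blinded study treatment and have microscopically-confirmed" *P. vivax* parasitaemia at baseline.

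SAP 11.7.2.2 adds that nobody in the mITT population is left out of any statistical analysis. The footnote to the fever listing (EFF_L3) confirms that men without baseline fever are carried as censored records with time zero. The objectives table in SAP 2.2, by contrast, defines the fever endpoint only for men with fever at baseline.

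**The concern.** The endpoints are times to clearance. Protocol 9.4.1 says that comparisons of parasite and fever clearance time will use survival methods. An event or no-event outcome asks whether a man ever cleared within the window. All arms receive DHA-PQP, so that is a different and much less informative question than how quickly he cleared. SAP 2.1 lists logistic regression as a change only for dichotomous endpoints, so this departure is not explained there.

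Censoring at time 0 is harmless in a Cox model, because such a man is never at risk. It is not harmless once the outcome is made binary: he has no clearance event, and nothing says he is to be removed. The SAP shows elsewhere that it can write such a rule. The logistic sensitivity analysis of the primary endpoint in 7.1.5.1 drops men censored before six months, and the missing-equals-failure analysis in 11.6.3 drops men with a zero baseline count.

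At stake is the between-arm comparison for fever and parasite clearance, two of the four endpoints under the blood-stage efficacy objective, and for gametocyte clearance.

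**Working it through.** Neither document gives a figure for these endpoints or their fallback, so there is nothing of the plan's own to reproduce here.

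**Inputs**
- 50 men per arm, 150 in all (Protocol 9.2.1; SAP 2.1 confirms that 150 were randomised).
- Clearance: "DHA-PQP has high efficacy rates (>95%) for clearing the blood stage infection of" *P. vivax* (Protocol 4.4). The values 98% and 99% below are assumptions within that range.
- Baseline prevalence *f* of fever or gametocytes: not given. Assumed to be 30%, 50% or 70%.
- Proportion clearing fever or gametocytes: not given. 95% is used for illustration.

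**Step 1. Fever and gametocytes, literal coding.** Never-affected men = 150 × (1 − *f*). Genuine failures = 150 × *f* × 0.05.

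| *f* | Never affected | Genuine failures | Never affected as share of non-events |
|---|---|---|---|
| 30% | 105 | 2.25 | 105/107.25 = 98% |
| 50% | 75 | 3.75 | 75/78.75 = 95% |
| 70% | 45 | 5.25 | 45/50.25 = 90% |

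Men with an inconsistent thermometer method would be added to the non-events; their number is unknown.

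**Step 2. Effect on a real difference.** Suppose 99% of affected men clear in one arm and 90% in the other. Among affected men the odds ratio is (0.99/0.01)/(0.90/0.10) = 11.0. With everyone included, the event probabilities become 0.99*f* and 0.90*f*. At *f* = 50% the odds ratio is (0.495/0.505)/(0.450/0.550) = 1.20. At 30% it is 1.14 and at 70% it is 1.33.

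**Step 3. Asexual parasites.** Baseline parasitaemia is an mITT requirement, so Step 1 does not apply. With clearance probability *p*, expected non-events per arm = 50(1 − *p*), and P(no non-event in an arm) = *p*^50. An arm with none gives an infinite, zero or undefined odds ratio in comparisons with it.

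| *p* | Non-events per arm | *p*^50 | At least one of three arms has none: 1 − (1 − *p*^50)³ | At least one of TQ and DHA-PQP only: 1 − (1 − *p*^50)² |
|---|---|---|---|---|
| 95% | 2.5 | 0.077 | 21% | 15% |
| 98% | 1.0 | 0.364 | 74% | 60% |
| 99% | 0.5 | 0.605 | 94% | 84% |

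**Step 4. Fever and gametocytes with unaffected men excluded.** This removes the miscoding but shrinks the sample. With 25 affected men per arm (*f* = 50%), 1 − (1 − *p*^25)³ is 62% at *p* = 95%, 94% at 98% and 99% at 99%. This is illustrative only, since the documents give no clearance rate for fever or gametocytes.

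**The case against.** Several stronger readings are tempting, and the documents do not support them.

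- **That all three endpoints are miscoded.** The mITT definition essentially removes the problem for asexual parasites.
- **That the SAP states the miscoding.** It does not. The coding is inferred from the time-0 censoring, the no-exclusion sentence and the absence of a rule, and it sits against the definition of the fever endpoint in SAP 2.2. Nor is the no-exclusion sentence applied literally everywhere, since one mITT logistic analysis does exclude censored men.
- **That the odds ratio is both contaminated and infinite.** For fever and gametocytes these are alternatives. With unaffected men included, the odds ratio is usually finite but says little about clearance. With them excluded, it may be sparse.
- **That nearly everyone clears fever and gametocytes.** The figure above 95% concerns blood-stage infection. Fever clearance needs a sustained normal temperature, and men not clearing by the last Day 3 assessment are censored, so genuine non-events may be commoner.
- **That the fallback will probably be used.** Nearly identical curves are compatible with a hazard ratio near 1, and chance crossing is not a violation. The double-dummy design has all arms start blinded drug on Day 1 or Day 2. Nothing supports a probability for the trigger.
- **That clearance speed disappears from the report.** Kaplan-Meier quartiles with confidence intervals and curves are planned for all three endpoints whatever model is used.

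All of this narrows the point. It does not justify the fallback, because under either coding the odds ratio does not measure speed of clearance.

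**Conclusion.** The point holds in a limited form. When triggered, the fallback replaces a time-based treatment contrast with one that ignores timing, contrary to Protocol 9.4.1 for parasite and fever clearance. For fever and gametocytes the handling of unaffected men is unspecified; read literally, they would form about 90% to 98% of non-events, given an assumed 30% to 70% prevalence and 95% clearance. For asexual parasites the weakness is sparseness: the chance that some arm has no non-event is 21% at the protocol's 95% floor, rising to 74% and 94% only if clearance is 98% or 99%. An infinite odds ratio is therefore a risk, not a certainty.

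The analysis is conditional on a visual judgement and concerns secondary endpoints. It does not affect the primary result.

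**What to change.** In SAP 7.2.5.1, remove the logistic fallback for the three clearance endpoints. State that the fever and gametocyte comparisons include only men with the condition at baseline. This leaves the Cox estimates unchanged, because men censored at time 0 are never at risk, but it settles the denominator. If hazards are judged non-proportional, report a time-based contrast alongside the Kaplan-Meier estimates already planned: for example, the difference in restricted mean clearance time with its 95% CI and a truncation time fixed in advance, or a battalion-stratified log-rank or Wilcoxon test.

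The cost is a few lines of SAP text and standard procedures. No new data and no protocol change are needed.
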